3.2 Exclusion Criteria

Patients who do not fulfill the criteria as listed in Section 3.1 above are ineligible.

3.3 Number of Participants to be Enrolled

A survey of investigators participating in the AMC consortium regarding the number of PEL patients seen at their site in the last 5 years reported 23 participants from 11 responding sites. By including the last 13 years (HAART era), it is reasonable to expect approximately 80 participants especially considering new sites added to the AMC.

3.3.1 Proposed Sample Size

The enrollment goal is 80 participants with a minimum of 20 participants in the genomics portion of the study.

3.3.2 Accrual Rate

An average of 4 participants per month anticipated.

3.3.3 Replacement of Participants in the Genomics Portion of the Study

A participant in the genomics portion of the study will be replaced if insufficient specimens are received (see Section 4.2.1.2 for required specimens), or if insufficient genetic material is retrieved (see Section 4.3.1). However, the participant may still participate in the clinical portion of the study if the eligibility criteria are met (see Section 3.1).

3.4 Participant Enrollment Procedures

This is a retrospective review. Enrollment is expected to occur over a two-year period. The medical records of participants who meet the inclusion/exclusion criteria will be reviewed. For participants enrolled into the genomics portion of the study, archived pathologic specimens will be obtained. Sites must obtain approval from their Institutional Review Boards (IRB) to waive the requirement for informed consent for this study, or conduct informed consent if required by the local IRB, and register with the AMC ODMC before enrolling participants.

After the investigator at the site has determined that a patient case is eligible for inclusion in this retrospective analysis, the participant will be registered for the protocol on-line via the AMC AdvantageEDCSM Internet Data Entry System. After successful registration, the participant will be assigned a system-generated ten-digit participant ID. Once the eligibility checklist is submitted, a system-generated confirmation email will be sent to the enroller upon successful completion of participant enrollment. If the online system is inaccessible, the site should notify the AMC ODMC (via email at [contact] or via phone at [contact]) for further instructions.

4.0 **RESEARCH METHODS**

4.1 Overview

Once an eligible case is enrolled on the protocol, the Primary Effusion Lymphoma Retrospective Analysis Forms will be available for data entry in the disease-specific Participant Assessment Form will be available for entry. The case report form will collect information regarding the participant's HIV/AIDS medical history, staging of AIDS related malignancy and type of treatment. Sites are to complete forms based on the participant's cancer diagnosis.

4.2 Study Plan

- 4.2.1 Data, Documents, Records, or Specimen Identification:
 - 4.2.1.1 The following data will be collected for participants enrolled into the clinical portion of the study:
 - HIV status, and for HIV-positive participants, include CD4 count, HIV viral load within one year prior PEL diagnosis (or within 3 months after PEL diagnosis)
 - Age at PEL diagnosis
 - Gender
 - Stage at PEL diagnosis
 - Treatment of PEL
 - Best response to PEL treatment
 - Survival status at 2 years post diagnosis
 - Pathology slides for central review (See Appendix II for specimen preparation and shipping)
 - Year of PEL diagnosis
 - 4.2.1.2 The following will be collected for participants enrolled into the genomics portion of the study:
 - Pathology slides for central review (if unavailable, paraffin block may be submitted)
 - Pathologic specimen that will be submitted for genomic analysis:
 - Frozen specimens, formalin-fixed and paraffin-embedded (FFPE) demonstrating PEL including cytospins as well as any mass/nodal biopsies are acceptable (See Appendix II for specimen preparation and shipping)
 - Survival status at 2 years post diagnosis
 - 4.2.1.3 The following is a list of additional data that is highly desirable for inclusion whenever available for participants enrolled in either the clinical and/or genomics portion of the study:
 - Race and ethnicity
 - For participants with HIV: HIV treatment history (which HAART drugs has participant received prior to PEL diagnosis, after PEL diagnosis), baseline HIV characteristics (i.e., CD4 count and HIV viral load closest

to time of PEL diagnosis, history of opportunistic infections)

- Presence or history of other human herpesvirus-8 (HHV-8)-related diseases (i.e., Kaposi's sarcoma, Multicentric Castleman's Disease), and other malignancies)
- Lymphoma baseline disease characteristics (immunophenotype, Epstein-Barr virus (EBV) and Kaposi sarcoma herpes virus (KSHV) status, sites of extranodal involvement), and either IPI or data required for calculation of International Prognostic Index (IPI)
- Lymphoma treatment: type, number of treatment regimens, use of therapeutic effusion drainage
- Best response to PEL treatment, best response duration
- Survival status at time of enrollment and duration of survival in months from PEL diagnosis

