2.0 BACKGROUND

2.1 Study Disease

Primary effusion lymphoma (PEL) is a rare type of non-Hodgkin lymphoma (NHL) that presents with predominately body cavity involvement and is nearly universally associated with Kaposi's sarcoma herpesvirus (KSHV), with Epstein Barr virus (EBV) also present in a fraction of cases¹. PEL is typically associated with a poor prognosis with a median survival of 6 months². A solid variant has also been described and carries a similarly poor prognosis³. PEL typically arises in the context of HIV infection, where it accounts for approximately 2-3% of AIDS-NHL².

Data supporting optimal treatment strategies of PEL are limited given the rarity of the disease. There are rare reports of remissions in PEL occurring with the introduction of HAART therapy in HIV patients, who are not on highly active antiretroviral therapy (HAART) at the time of diagnosis. However, HAART is not sufficient for adequate treatment in the vast majority of AIDS-PEL cases. Therefore, combined chemotherapy regimens and other anti-viral treatments are now routinely used for AIDS-PEL treatment. In addition to classic CHOP-based chemotherapy, clinicians and investigators have employed one or more of the following: (a) infusional chemotherapy regimens (EPOCH); (b) methotrexate (after chemotherapeutic debulking or drainage of effusions); (c) VEGF inhibition, aggressive effusion drainage; (d) taken advantage of latent gamma herpes virus tumor infection using bortezomib as an inducer of lytic viral replication and an inhibitor of $NF-kB^4$; and (e) cidofovir or valganciclovir as inhibitors of KSHV replication, with or without interferon⁵. Auto- and allo-geneic hematopoietic stem cell transplant is also reported in the salvage setting with variable success. Long-term AIDS-PEL survivors have been reported², some of whom are being followed at UCSD as well as by collaborators at other institutions within the AMC.

Most of the literature on AIDS-PEL is in the form of single or small case reports, with the largest series including 28 participants reported from a French cohort in 2005^2 . This series explored baseline clinical factors associated with poor survival and identified ECOG performance status > 2 and lack of HAART use at time of diagnosis as independent predictors of shorter survival. A recent review of case in the literature identified the number of body cavity sites as predictive of survival⁶.

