An initial genomic evaluation of 9 PEL cases was published by Klein et al., in 2003 and reported PEL as having a distinct profile from other NHLs – including those from immunocompetent and HIV-seropositive hosts – with features of both immunoblasts and plasma cells⁷. Although distinct, AIDS-PEL had a profile most similar to EBV+ immunoblastic diffuse large B cell lymphoma. Despite the limited sample size, they were able to identify 51 genes differentially expressed between PEL cells and normal B cells as well as NHL, including AIDS-NHL.

Past work on gene expression profiling of AIDS-PEL determined that it was quite different from other types of non-HIV and AIDS-related non-Hodgkin's lymphoma⁷ and discerned sub-types of PEL that were primarily associated with the presence, or absence of either KSHV or EBV⁸. In the first study, 9 cases of fresh AIDS-PEL specimens, in the form of cell blocks prepared from cytospins of the PEL fluid, were expression profiled on the Affymetrix U95 GeneChip. Although distinct, AIDS-PEL had a profile most similar to

EBV+ immunoblastic diffuse large B cell lymphoma. Despite the limited sample size, they were able to identify 51 genes differentially expressed between PEL cells and normal B cells as well as NHL, including AIDS-NHL. In the second study, 3 cases of freshly obtained AIDS-PEL mononuclear cells were expression profiled on the Affymetrix U133 GeneChip. In contrast, the intent of this project is to identify genes in PEL, whose expression is associated with long-term survival (≥ 2 years).

Currently, little is known about factors of prognostic importance in PEL. We hypothesize that there will be a sub-set of PEL clinical characteristics and differentially expressed genes in PEL cells that will be of prognostic value for this disease, when data from long-term and short-term survivors of the disease are compared.

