3.1 Eligibility Criteria

Patients diagnosed with primary effusion lymphoma (HIV seropositive or negative) on or after January 1, 1998 on whom survival status at 2 years post PEL diagnosis is available.

Participants may be enrolled to *either or both* the clinical or genomic portions of the study.

The minimum data required to be able to include a participant for analysis of **clinical prognostic factors** are:

- a. HIV status, and for HIV-positive participants, include CD4 count, HIV viral load within one year prior PEL diagnosis (or within 3 months after PEL diagnosis)
- b. Age at PEL diagnosis
- c. Gender
- d. Stage at PEL diagnosis
- e. Treatment of PEL
- f. Response to PEL treatment
- g. Survival status at 2 years post diagnosis
- h. Pathology slides (or paraffin block) for central review
- i. Year of PEL diagnosis

The minimum data required to be able to include a participant for analysis of **genomic prognostic factors** are:

- a. Availability of a pathologic specimen of PEL that will be submitted for genomic analysis
- b. Survival status at 2 years post diagnosis

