The general approach to RNA-Seq data analyses is as follows: Multiplexed RNA-Seq data will be deconvoluted to separate each of the samples, after which, sequencing adapters and poly-A/T tails will be trimmed using cutadapt software. Sequencing reads of length less than 20 base pairs will be removed. Reads will be aligned to the human genome using STAR software. Aligned reads will be realigned using GATK's IndelRealigner. Gene Expression: STAR genomic alignments will be filtered to remove any reads that align outside of Gencode exons. Remaining reads will be realigned to the Gencode transcriptome using bowtie2 and transcriptome alignments passed to eXpress for expression estimation. Gene expression will be calculated by summing the FPKM estimates for each of the gene's transcripts. Genes with expression greater than zero FPKM will be considered expressed. All of the RNA-Seq data that pass these quality metrics will then be normalized and then subjected to supervised analysis to identify genes differentially expressed between PEL treatment responders vs non-responders. This supervised analysis will be performed by means of t-test with multi-testing correction (Westfall & Young Permutation method)¹¹ (p < 0.05, FDR < 0.05). Based on past experience¹⁰, we expect that fewer than 500 genes will be found to be differentially expressed between treatment responders and non-responders. Lastly, we will take advantage of bioinformatic approaches to examine genes that are found to be differentially expressed between the sample groups. software. Bioinformatic such as Ingenuity Pathways (http://www.ingenuity.com), focus on the analysis of genetic networks and pathways and help place such genes, which may have prognostic significance, into biologic context.

Following quantification and quality assessment of the RNA, RNA-Seq analyses, as described above will be performed on 20 PEL specimens, 10 of which are from long-term survivors and 10 from non-long-term survivors. The resulting data will be assessed for quality and adequacy: the total number of reads compatible with a transcript on the RNA-Seq assay.

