5.0 STATISTICAL CONSIDERATIONS

5.1 Study Design/Endpoints

5.1.1 Analysis/Statistics

Survival will be estimated using the Kaplan Meier method and Cox proportional hazards model will be used to assess differences between treatment groups and categorical baseline variables. Response rates will be reported with 95% confidence intervals (binomial distribution). Descriptive statistics will be used to summarize baseline clinical, histological, and viral characteristics.

We will perform either RNA-Seq or GeneChip assays, as described in Section 4.3, expression profiling on a total of up to 80 AIDS-PEL specimens. We are already aware of at least 10 long -term AIDS-PEL survivors within the AMC. Resultant data will be assessed for quality, normalized, and then analyzed for differential gene expression. We will use standard algorithms in both GeneSpring and Bioconductor for this purpose, with which we have considerable experience (see Preliminary Studies above). In particular, the RNA-Seq data will be analyzed by the DESeq algorithm in Bioconductor¹. Lastly, we will take advantage of bioinformatic analysis approaches to help make sense of possible biological links between the genes found to be differentially expressed between the sample groups that may be of prognostic significance. These bioinformatic approaches, such as Ingenuity Pathways (http://www.ingenuity.com), focus on the analysis of genetic networks and pathways and help place genes identified as differentially expressed into biologic context.

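### EBV status, which the protocol links to PEL expression sub-types, is optional for genomic cases and absent from the survivor contrast, so EBV markers cannot be separated from EBV-independent survival genes

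*Combined protocol and SAP*

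**What the plan says.** Section 2.1 reports that earlier profiling "discerned sub-types of PEL that were primarily associated with the presence, or absence of either KSHV or EBV". It describes KSHV as nearly universal in PEL, "with Epstein Barr virus (EBV) also present in a fraction of cases". EBV is therefore the virus that varies usefully between cases.

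Section 3.1 sets two minimum items for a genomic case: "Availability of a pathologic specimen of PEL that will be submitted for genomic analysis", and survival status at 2 years. Section 4.2.1.2 adds slides for central review. Viral status appears only in 4.2.1.3, as "Epstein-Barr virus (EBV) and Kaposi sarcoma herpes virus (KSHV) status, sites of extranodal involvement", under a list introduced as "additional data that is highly desirable for inclusion whenever available for participants enrolled in either the clinical and/or genomics portion of the study".

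The comparison is described twice. Section 4.3.2.1 gives a two-group t-test with Westfall-Young correction and thresholds of p < 0.05 and FDR < 0.05. Section 5.1.1 says "the RNA-Seq data will be analyzed by the DESeq algorithm in Bioconductor", without a design formula. Neither names a covariate, stratum or matching factor. Viral characteristics are assigned only to descriptive summary in 5.1.1.

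**The concern.** The primary genomic objective is a list of genes associated with survival of 2 years or more. The protocol itself identifies one axis along which PEL expression differs, then neither secures that information for genomic cases nor uses it in the comparison.

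Two things are at stake:

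- **Interpretation.** If the EBV-positive share differs between survivors and non-survivors, genes that track EBV will differ between the groups as well. Without EBV status, nobody can tell whether a listed gene says anything beyond the patient's EBV status.
- **Power.** If the share is the same in both groups, EBV-related variation sits in the error term and makes true survival genes harder to find among those that EBV affects.

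No other section closes the gap. Central review (4.3.1) covers morphology, immunophenotype and tumour percentage, and does not name EBV typing. Section 4.3.2.3 mentions viral RNAs as a possible insight, but the pipeline in 4.3.2.1 aligns reads to the human genome and drops reads outside Gencode exons.

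**Working it through.** The documents give no power calculation, EBV prevalence or EBV effect size, so there is no stated figure to reproduce. What follows is illustration on assumed values.

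**Inputs from the protocol.** The RNA-Seq comparison is 10 v 10 (4.3.2.1). Up to 80 specimens may be profiled (5.1.1). Long-term survivors are put at 25–40% in 4.3.1 (0.25 × 80 = 20 to 0.40 × 80 = 32) and at 15–25% in 5.2 (0.15 × 80 = 12 to 0.25 × 80 = 20). Both ranges are used.

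**Assumptions.** EBV-positive: 50% of survivors and 80% of non-survivors. EBV shifts a gene by d = 1.5 SD (range 1 to 2). The gene has no survival effect within EBV strata. Two-sided t-tests stand in for the planned methods.

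**Step 1: false attribution, one gene, unadjusted p<0.05.**

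- Expected group difference: 1.5 × (0.80 − 0.50) = 0.45 SD.
- Variance in survivors: 1 + 1.5² × 0.5 × 0.5 = 1.5625. In non-survivors: 1 + 1.5² × 0.8 × 0.2 = 1.36.
- 10 v 10: SE = √(1.5625/10 + 1.36/10) = 0.541; 0.45/0.541 = 0.83. The normal approximation gives about 13% rejection.
- 20 v 60: SE = √(1.5625/20 + 1.36/60) = 0.317; 0.45/0.317 = 1.42. The normal approximation gives about 29%.

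Simulation agrees:

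| Survivors v non-survivors | No EBV term | EBV in model |
|---|---|---|
| 10 v 10 | 13% | about 5% |
| 12 v 68 | 24% | about 5% |
| 20 v 60 | 31% | about 5% |
| 32 v 48 | 37% | about 5% |

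At 10 v 10 the unadjusted figure is 9% for d = 1 and 16% for d = 2.

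**Step 2: after multiplicity correction.** Assume 10,000 genes, 500 of them EBV-related, and Benjamini-Hochberg FDR 0.05 as a proxy for the planned correction.

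- 10 v 10, same shares as above: at least one EBV-related gene is selected in about 3% of runs at 1.5 SD and 4% at 2 SD. At a Bonferroni-type cut-off of 0.05/10,000 = 0.000005, a given EBV-only gene (1.5 SD) passes in about 0.008% of comparisons.
- 20 v 60, 2 SD, shares of 85% (survivors) v 55%: at least one gene is selected in about 18% of runs. At 90% v 50% it is about 55%, with a mean of about 41 genes flagged. With equal shares it is about 5%.

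**Step 3: equal EBV prevalence.** With the same share in both groups, the average unadjusted error rate stays at about 5%. A single draw can still be uneven: the groups of 10 differ by at least 3 EBV-positive cases in 22% of draws at a share of 0.3 or 0.7, and in 26% at 0.5.

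**Step 4: power with equal prevalence.** With half of each group's source population EBV-positive (q = 0.5) and d = 1.5, EBV accounts for q(1−q)d²/(1 + q(1−q)d²) = 0.5625/1.5625 = 36% of the gene's variance (20% at d = 1, 50% at d = 2). The SD rises to √1.5625 = 1.25, so a true 1 SD survival effect acts like 1/1.25 = 0.8 SD. Simulated single-gene power at 10 v 10 and unadjusted p<0.05 is about 39% without EBV in the model and 54% with it. For a gene EBV does not affect, adding the term costs little: 56% falls to about 53%.

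**The case against.** The strongest reply is that the objective asks for genes associated with survival, not for genes associated independently of EBV. If EBV is itself prognostic, a gene that marks EBV is a genuine correlate of survival, and an EBV-adjusted model used alone would change what is estimated. That stands. It is why the adjusted analysis should sit beside the unadjusted one and not replace it.

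Other parts of the reply also stand. A reader might infer that EBV-related genes will fill the 10 v 10 list. The single-gene 13% ignores the planned multiplicity correction, under which the risk at that size is small. A reader might infer that chance imbalance inflates the error rate; on average it does not, although the one list obtained can mislead. A reader might also infer that viral status drives PEL expression. Section 2.1 reports an association from earlier work, and the second study it describes had 3 cases. KSHV, being nearly universal, offers almost no contrast.

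The reply adds that viral status is already requested and that no DESeq formula is fixed, so adjustment remains possible. That does not answer the point. An item collected only when available may be missing for many genomic cases, and an adjustment chosen after seeing the data is weaker than a prespecified one.

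**Conclusion.** The point holds as a limit on interpretation and power. As planned, the gene list cannot separate EBV markers from EBV-independent survival genes if EBV prevalence differs between survivor groups, and it loses power in EBV-affected genes if prevalence is equal. No passage says that EBV prevalence does differ by survival, so the documents do not support a claim that the list will be wrong.

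The false-attribution risk matters mainly in the larger set of up to 80 specimens. The power loss applies at 10 v 10 as well and needs no link between EBV and survival. All sizes rest on assumed EBV shares and effects, and on t-tests and Benjamini-Hochberg as stand-ins for DESeq and Westfall-Young. The absence of a viral term does not depend on which contrast is meant: 4.3.2.1 words it as treatment responders v non-responders while the objective uses survival, and neither version has one. This is a change that should be made, not one that invalidates the study.

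**What to change.** - **Section 4.2.1.2:** make EBV status a mandatory field for genomic cases (positive, negative, unknown), taken from the pathology report where it is stated. Appendix II already requires that report, but does not say that it contains EBV results, so the unknown code is needed.
- **Section 3.1:** leave unchanged. Sections 3 and 3.2 make any unmet criterion exclusionary without exceptions, so a requirement there could lose cases of a rare disease.
- **Section 5.1.1:** keep the unadjusted survivor contrast. Add a prespecified DESeq analysis with EBV status as a covariate among cases with known status. Report for each selected gene whether it also differs by EBV status.

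The cost is one degree of freedom, a smaller adjusted set where EBV is unknown, and a little more analysis work. The field is best completed while specimens are in hand, since Appendix II returns slides and blocks to the sites once studies are complete.

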4.3 Genomics Methods

4.3.1 RNA Extraction and Quality Assessment

The vast majority of specimens are in the form of archived blocks of cells prepared from cytospin of PEL fluid that are formalin-fixed and paraffin-embedded (FFPE). Each specimen will be centrally reviewed for morphology and immunophenotype to confirm the diagnosis of PEL and to ascertain the percentage of tumor cells in the tissue block. Only samples containing > 95% PEL cells will be further profiled. It should be noted that PEL effusions are typically quite homogeneous, such that all 9 of the specimens assessed by Klein et al. met this criteria⁷. Thus, we expect that nearly all of the FFPE PEL specimens received for this study should be able to move forward for expression profiling. Based on our experience and feedback from outside AMC investigators, we expect that 25-40% of the PEL samples will be from patients who are long-term survivors (20-32 of the 80 total PEL specimens).

Total RNA will be extracted from FFPE PEL sections using a method that enables preparation of RNA for use in both microarray and RNA-Seq assay protocols (i.e., Prelude FFPE Isolation Module (NuGen Inc.)). Some 5 x 20 micron sections of the trimmed FFPE blocks will be extracted by column purification following deparaffinization and lysate preparation. RNA quantity will be measured by OD 260/280/320 assay on a NanoDrop spectrophotometer. Although we anticipate the RNA to be variably degraded, we will still assess its quality by determining a RIN score following Bioanalyzer assay. This will permit us to determine whether a very poor RIN metric (i.e., < 7) was instrumental in the outcome of an expression assay and enable better comparison of the results. We will use enough of each PEL specimen to prepare approximately 400 ng of total RNA. The RNA will be stored at -80°C.

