4.3.2.3 Analytic Strategy

RNA-Seq assay of PEL is the preferred approach because it has a better linear dynamic range than does a GeneChip assay and may provide insights about PEL genomics that are not possible to be discerned by GeneChipbased expression profiling (i.e., novel splice junctions and transcripts, viral RNAs, etc.). However, because of the high likelihood of very substantial RNA degradation in these FFPE samples, we are concerned about the potential for poor quality RNA-Seq data. RNA-Seq will be the primary method for genomic analysis of the PEL specimens, if it satisfies QC metrics for read number and data quality (i.e., 30 million pair-end reads of length > 30 nucleotides, of which 20-25 million may be mapped to the genome or known transcriptome; R^2 (Pearson) correlation between technical replicates of the same sample of > 0.9). If the QC metrics are not met, GeneChip assay will be performed instead, as these should yield higher quality data. In summary, GeneChip assay is planned as a backup in the event that RNA-Seq QC is inadequate.

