APPENDIX II: SPECIMEN PREPARATION AND SHIPPING INSTRUCTIONS BACKGROUND AND PROCEDURES

The following specimens are required for participation in the genomics portion of the study:

- Paraffin embedded tissue or cytology block or frozen tissue specimen (latter preferred if available).
- Pathology slides and a pathology report for central pathology review. If slides are not available, the site must provide a paraffin block for review, which if adequate, will also be used for genomic studies. The participant can be included in the clinical portion of the trial if the material submitted is only sufficient for pathology review.
- If neither slides nor adequate paraffin block is available, the participant will be considered ineligible.

For participants in the clinical portion, pathology slides and a pathology report are required for central pathology review.

Slides and/or tissue blocks will be returned to the site once all studies are complete.

Details regarding specimen shipment are provided in the protocol Manual of Procedures.

Technical questions regarding tissue specimens should be directed to [name] (see Protocol Roster).

The AMC Biorepository will ship pathology slides and tissue specimens to UCSD and Cornell for central pathology review. Specimens for genomic analysis will be sent to UCSD.

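### RNA degradation is expected to vary and RIN is measured, but neither expression analysis adjusts for it, so degradation could pass as a survival signal if it differs between survivor groups

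*Combined protocol and SAP*

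**What the plan says.** Section 4.3.1: "Although we anticipate the RNA to be variably degraded, we will still assess its quality by determining a RIN score following Bioanalyzer assay". It then gives the purpose: "This will permit us to determine whether a very poor RIN metric (i.e., < 7) was instrumental in the outcome of an expression assay". The same sentence goes on to say that RIN should also help in comparing results. No covariate, stratum or exclusion based on RIN appears anywhere.

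Section 4.3.2.3 is cautious about RNA-Seq "because of the high likelihood of very substantial RNA degradation in these FFPE samples". Its safeguards are read-number and mapping thresholds, a replicate R² above 0.9, and GeneChip as backup. Section 4.3.2.2 adds a present-call cut-off and a GAPDH 3'/5' ratio for arrays.

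Section 3.1 admits patients diagnosed "on or after January 1, 1998 on whom survival status at 2 years post PEL diagnosis is available". Section 4.2.1.2 and Appendix II accept both frozen and FFPE material.

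On analysis, Section 4.3.2.1 names a two-group t-test with Westfall-Young correction, worded for treatment responders against non-responders. It also says that RNA-Seq will be "performed on 20 PEL specimens, 10 of which are from long-term survivors and 10 from non-long-term survivors", without saying how those specimens are picked. Section 5.1.1 allows profiling of up to 80 specimens and states that "the RNA-Seq data will be analyzed by the DESeq algorithm in Bioconductor", with no design formula.

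**The concern.** The primary genomic objective is to find genes associated with survival of two years or more. The plan itself treats degradation as the main threat to data quality and measures it, but leaves it out of the comparison. If one survivor group's RNA is more degraded on average, genes whose measured level depends on RNA quality will differ between the groups for technical reasons.

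The listed safeguards do not address this:

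- The quality thresholds pass or fail a sample or an assay. They do not balance degradation among the samples that pass.
- The triplicate libraries come from the same RNA sample, so they can agree closely while sharing the same bias.
- The GeneChip fallback would use RNA from the same specimens.
- Westfall-Young controls multiplicity. It does not remove a confounder that travels with the group label.

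**Working it through.** **Inputs from the documents.** The initial set is 10 v 10 (4.3.2.1), and up to 80 specimens may be profiled (5.1.1). Section 4.3.1 expects 25-40% long-term survivors: 0.25 × 80 = 20 and 0.40 × 80 = 32, which reproduces its 20-32. Section 5.2 says 15-25%, which is 12-20. The two estimates meet only at 25%, so 20 v 60 stands for the full set. The genomic part gives no power calculation, effect size or RIN distribution.

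**Assumptions.** r is the within-group correlation between a gene's expression and RNA quality Q. D is the difference in mean quality between survivor groups, in SD. The model is y = rQ + √(1−r²)·e, with no survival effect. Neither r nor D is in the documents.

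**Step 1: one gene, unadjusted two-sided t-test at 5%.** The spurious difference is rD in SD units. The noncentrality is rD × √(n₁n₂/(n₁+n₂)). The root is √(100/20) = 2.236 at 10 v 10 and √(1200/80) = 3.873 at 20 v 60.

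| Split | r | D | Noncentrality | Chance of p < 0.05 |
|---|---|---|---|---|
| 10 v 10 | 0.7 | 0 | 0 | 5% |
| 10 v 10 | 0.3 | 0.5 | 0.335 | 6% |
| 10 v 10 | 0.5 | 1 | 1.118 | 19% |
| 10 v 10 | 0.7 | 1 | 1.565 | 32% |
| 20 v 60 | 0.7 | 1 | 2.711 | 76% |

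Simulation agrees with these rates. In the rows with D above 0, regression on group plus Q gives about 5%. The bias grows with sample size, so profiling more specimens does not cure it.

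**Step 2: with the plan's correction.** This simulation used 1,000 genes, 20% of them linked to RIN, r = 0.7, no true survival effect, and 200 to 500 runs per scenario.

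- Westfall-Young at 10 v 10, chance of any false gene: 5% (D = 0), 7% (D = 0.5), 20% (D = 1), 52% (D = 1.5).
- Westfall-Young at 20 v 60, D = 1: 77%.
- Unadjusted Benjamini-Hochberg at D = 1: on average 7 false genes per 1,000 at 10 v 10, and 89 at 20 v 60.
- Adjusted for RIN, with Benjamini-Hochberg at 0.05: chance of any false gene between 4% and 9% in all scenarios, close to nominal for this number of runs.

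**Step 3: what adjustment costs or gains.** Take a true 1.5 SD difference at p < 0.001, 10 v 10. The noncentrality is 1.5 × 2.236 = 3.354, and unadjusted power is 34%.

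- Genes not sensitive to degradation (r = 0): adjusted power is 30% at D = 0, 27% at D = 0.5 and 21% at D = 1.
- Sensitive genes with balanced groups (D = 0): adjusted power is about 35%, 45% and 71% at r = 0.3, 0.5 and 0.7.

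**Step 4: if RIN measures quality poorly.** With an assumed reliability of 0.5 and D = 1, the adjusted false-positive rate at 10 v 10 is about 8% (r = 0.5) and 12% (r = 0.7). That is better than 19% and 32%, but not nominal.

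**Step 5: chance imbalance.** The SD of a difference in mean quality at 10 v 10 is √(2/10) = 0.447. An imbalance of at least 0.5 SD is 0.5/0.447 = 1.118 standard errors or more, which happens in 26% of sets. This does not raise the long-run error rate, but it is a reason to show RIN by group.

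**The case against.** The strongest reply is that the harm is conditional. No section gives RIN or diagnosis year by survivor group, and none says that older blocks hold more degraded RNA. Section 2.2 starts eligibility in 1998 because HAART use was widespread from then, which limits one era effect. At D = 0 the planned test is valid, and in the mild case (r = 0.3, D = 0.5) the rate is 6%. All of this stands. On the other side, the cohort described in Section 2.1 found that lack of HAART at diagnosis predicted shorter survival. A link between calendar era and survival is therefore plausible, though not shown.

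Three stronger readings are tempting and lack support:

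- A reader might infer that RIN serves only as a look-back on assay failure. The sentence in 4.3.1 also states a comparative aim. What is missing is the method.
- A reader might infer from the genomic minimum-data list in 3.1, which omits year of diagnosis, that block age could be unknown for genomic-only cases. Eligibility for every participant rests on the diagnosis date and on status two years later, and Section 7.1 names year of diagnosis among the dates collected.
- A reader might turn the per-gene rates into a large count of false genes at an uncorrected p-value. The plan uses Westfall-Young and an FDR limit, so the corrected figures in Step 2 are the relevant ones.

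It is also fair to say that the library kit is chosen for degraded FFPE RNA, that data are normalized, and that Section 2.2 presents the study as a lead-in to prospective work. These points reduce the stakes, but none of them balances degradation between survivor groups.

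**Conclusion.** The concern holds in conditional form. The plan foresees variable, substantial degradation and measures it, but neither stated analysis uses the measure and the 10 v 10 set has no selection rule. That bias is actually present cannot be concluded from the documents.

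The sizes rest on assumed values of r and D. At a 1 SD group difference the unadjusted test is clearly unsafe: roughly four to six times the nominal per-gene rate at 10 v 10 (19/5 to 32/5), about fifteen times at 20 v 60 (76/5), and about four times the nominal family-wise rate under Westfall-Young at 10 v 10 (20/5). At half that difference the excess is small at 10 v 10. At zero there is none. Adjustment restores about 5% only if the score measures quality well.

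The change should be made because it protects the primary genomic objective with a measurement already planned. The survivor contrast also needs writing down in any case, since the t-test in 4.3.2.1 is worded for response rather than survival.

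**What to change.** 1. In both 4.3.2.1 and 5.1.1, and for the GeneChip fallback, define the contrast as long-term against non-long-term survivors in all profiled specimens. Include continuous RIN, or another degradation measure named in advance, as a covariate. If Westfall-Young is kept, state how the permutation respects the covariate, for example by permuting residuals from the RIN-only model.
2. Report the chosen measure by survivor group, and give the unadjusted result as a sensitivity analysis.
3. Where more than 10 non-long-term survivor specimens are available, choose the 10 within diagnosis-year bands similar to those of the long-term survivors, using the year already needed for eligibility. This helps only the 10 v 10 set. The larger analysis depends on the covariate.

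Cost: SAP wording, one model degree of freedom (18 to 17 at 10 v 10) and a selection step. No new assay is needed if RIN is used. The real price is power for genes not sensitive to degradation: 34% to 30% if the groups are balanced, and to 21% at a 1 SD imbalance (Step 3). If RIN proves a poor measure, part of the bias remains, and the report should say so.
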